7.1.4.6 Estimate Glomerular Filtration Rate (eGFR)

A derived calculation of eGFR will be calculated using the 4 variable Modification of Diet in Renal Disease (MDRD) equation (Lavey 1999 and 2000):

$$\text{eGFR (mL/min/1.73m}^2\text{)} = 175 (\text{Serum Creatinine in } \mu\text{mol/l} \times 0.011312)^{-1.154} \times (\text{age})^{-0.203} \times (0.742 \text{ if female}) \times (1.212 \text{ if African/American Black})$$

7.2 Handling of missing data and outliers

7.2.1 Missing data analysis methods

Unless specified, data in summary tables will be presented using Observed Case (OC) data and therefore no missing data will be imputed.

The primary endpoint will be performed using both a last observation carried forward (LOCF) imputation and non-responder imputation (NRI). For the LOCF approach, subjects with missing testosterone value at a visit will be imputed with the last non-missing, post-baseline testosterone value. This value will then be used to determine if the subject achieved normalisation at that visit. For the NRI approach, subjects with missing testosterone value at a visit will be deemed as not achieving testosterone normalisation at that visit.

For each continuous secondary endpoint, the change from Baseline will be assessed with a mixed model repeated measure (MMRM) analysis.

For data listings, unless specified, all data will be presented as they have been recorded (e.g. missing and partial dates will not be replaced).

7.2.2 Handling of missing or incomplete data

7.2.2.1 Partial dates of first HH diagnosis

In order to calculate the HH disease duration (i.e. time since first HH diagnosis), the following rules will be applied for partial dates for first diagnosis of HH:

- if the day of the month is missing it is imputed to be the 15th
- if both the day and month are missing, they are imputed to be June 30th
- missing years will be left as missing.

The above will be flagged and described as a footnote in the appropriate listings.

7.2.2.2 Missing items within Questionnaire data

The method of handling missing data for each questionnaire will be based upon the author's recommendation. Details can be found in Section 7.1.3.

7.2.2.3 Missing or incomplete concomitant medication dates

Should the start date for a medication/procedure be missing or incomplete to the extent that it could be before or after the time of start of study medication, then it will be assumed that the medication/procedure began after the start of study medication (i.e. reported as concomitant medication/procedure). Similarly, if it is not clear whether the medication/procedure start date was on or before, or after the Visit 8 date, then it will be assumed the medication/procedure began on or before the Visit 8 date (i.e. reported as a concomitant medication/procedure) (worst case approach).

7.2.2.4 Definition of treatment-emergent AEs and handling of missing or incomplete dates

In the event of an incomplete onset date, the event will be considered to be treatment-emergent unless the partial onset date information or complete or partial end date confirms onset or end prior to the first dose of study medication date (or after the date entering the extension study for those that continue into the extension study).

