12.1.2 Recording of Adverse Events

For the purposes of this study, only SAEs will be collected during Screening Period (the time between signing the ICF and randomisation).

Any detrimental change in the subject's condition, after randomisation and up to 90 days after the last administration of study drug should be considered an AE.

The following variables will be recorded for each AE: verbatim/AE description and date for AE start and stop, severity, seriousness, causality rating, whether or not the AE caused the subject to discontinue, and the outcome. If the severity of the AE changes, a new AE must be recorded.

SAEs and AEs will be recorded after randomisation. SAEs only will be reported during the screening period (from signing of the informed consent to randomisation). All AEs/SAEs

have to be reported, whether or not considered causally related to the investigational product or to the study procedure(s).

All ongoing AEs/SAEs should be followed up until resolution or stabilisation or the last visit if in the investigator's opinion, the AE is unlikely to resolve due to the subject's underlying disease.

At any time after the FU visit, if an investigator learns of an SAE that can be reasonably related to study drug, he/she should promptly notify the sponsor.

Intensity

The investigator will assess the intensity of AEs based on the following definitions:

1. Mild (awareness of sign or symptom, but easily tolerated)
2. Moderate (discomfort sufficient to cause interference with normal activities)
3. Severe (incapacitating, with inability to perform normal activities).

It is important to distinguish between serious and severe AEs. Severity is a measure of intensity whereas seriousness is defined by the criteria in [Section 12.1.8](#).

An AE of severe intensity need not necessarily be considered serious. For example, nausea that persists for several hours may be considered severe nausea, but not an SAE. On the other hand, a stroke that results in only a limited degree of disability may be considered a mild stroke but would be an SAE.

For an AE to be a suspected drug-related event there should be at least a reasonable possibility of a causal relationship between the study drug and the AE.

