3 STUDY DESIGN

3.1 General study design

This is a phase IIb, multicentre, double-blind, randomised, placebo-controlled parallel-group 36-week study evaluating safety and efficacy of BGS649 in male obese subjects with hypogonadotropic hypogonadism (HH). The study will have three phases:

1. A Screening Phase lasting up to 28 days, including Day -28 to Day -1
2. A Randomisation Phase including the Baseline visit (Day 1) and the treatment period Day 1 to Visit 8 (Week 24)
3. A Safety Follow-Up Phase to Visit 11 (Week 36, follow-up [FU]). Visits 9 and 10 are telephone assessments

Study participation will comprise up to 2 Screening Visits, 8 visits during the treatment period up to Week 24 (End of Treatment [EOT]), FU Visits 9, 10 (telephone assessment) and 11 (at Weeks 28, 32 and 36 respectively) for safety performed to 12 weeks after Visit 8 (EOT).

[figure not shown]
Eligible subjects will be randomised on Day 1 (Baseline) in a 1:1:1:1 ratio to one of the following treatment groups, consisting of [REDACTED]

- o BGS649 [REDACTED]
- o BGS649 [REDACTED]
- o BGS649 [REDACTED]
- o BGS649 matching placebo [REDACTED].

Once approximately 100 of the overall planned enrolled subjects have completed the Week 4 visit, an interim analysis will be performed by an independent DMC who will determine whether the criteria for normalisation of testosterone (testosterone within or above normal reference range for healthy adult males according to FDA criteria) were met. Dosing arms which met this criterion will be deemed effective. For dosing arms deemed to be ineffective, dosing will be stopped and no further randomisation to that arm will be performed. See Section 8.8.1.2 for full details of the Interim Analysis.

A minimum of 25 subjects per treatment arm will be invited to participate in a 6 month extension study (Protocol MBGS206), starting at Visit 8 (EOT). Subjects participating in the 6 month extension will have their last study visit at Visit 8 (EOT) and will not participate in Visits 9, 10, and 11.

Figure 1: Study Flow Chart

D=day; DMC=Data Monitoring Committee; EOT= End of Treatment; IRT=Interactive response technology; PK, pharmacokinetic; W=week

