7.1.4 Definitions relative to safety parameters

7.1.4.1 Adverse Event (AE)

Treatment Emergent Adverse Event (TEAE)

A Treatment Emergent AE (TEAE) is defined as an AE occurring or worsening on or after the first dose of study medication. For subjects that enter the extension study, only AE's occurring prior to entering the extension study will be considered a TEAE and summarised.

TEAEs will also be split between AEs that start during the treatment period and those that start on or after the first day of the follow-up period (for subjects not entering the extension study).

Duration of AEs

The duration of an AE will be calculated as the resolution date minus the start date plus 1.

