7.1.4.3 Prior, Concomitant and Follow-up Medications/Procedures

Medications and Procedures will be assigned as being prior to study treatment, concomitant with study treatment or taken during the follow-up phase based on the start and stop dates of the medication and dosing dates.

If the medication/procedure stop date is before the date of the first dose of study medication, the medication/procedure will be assigned as being prior to study treatment. Otherwise, the medication/procedure will be assigned as being concomitant with study treatment unless the start date of the medication/procedure is after the Visit 8 date, when it will then be classified as occurring in the follow-up phase. For subjects that enter the extension study, only medications/procedures with a start date prior to entering the extension study will be categorised and summarised.

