8.7.1 Adverse events

All AEs will be classified by SOC and PT according to the MedDRA Version 19.1 or higher.

Details for imputing missing or partial start dates of adverse events are described in Section 7.2.2.4.

All AE summaries will be generated by treatment period, follow-up period and overall (i.e including those that started in both the treatment period and follow-up period).

Notes:

- Two AEs with the same PT will be considered as two different events when calculating the “number of events” in the tables.

- Where a subject has the same AE, based on preferred terminology, reported multiple times in the same category the subject will only be counted once at the preferred terminology level in AE frequency tables.
- Where a subject has multiple AEs within the same SOC in the same category, the subject will only be counted once at the SOC level in AE frequency tables.
- AEs where the intensity is missing will be assumed to be “Severe”
- AEs where the causality is missing will be assumed to have “Reasonable possibility of relatedness”

An overall summary of AEs will be provided. The total number of events and number and proportion of subjects experiencing any AEs, TEAEs, TEAEs of special interest, AEs related to study medication (i.e where the investigator has recorded “Reasonable possibility of relatedness”), SAEs, SAEs related to study medication, severe AEs, AEs leading to permanent discontinuation of study treatment and AEs leading to death will be tabulated for each treatment regimen and overall.

Additionally, TEAEs, TEAEs of special interest, related TEAEs, serious TEAEs, related SAEs, AEs leading to permanent discontinuation of study treatment and AEs leading to death will be summarised by SOC and PT for each treatment regimen and overall (number and percentage of subjects experiencing at least one AE per PT as well as the number of observed events per PT). All TEAEs will also be summarised separately by maximum intensity for each SOC and PT and by causality for each SOC and PT.

A table presenting the number and percentage of subjects with at least one AE and the number of AEs for the most common treatment-emergent AEs (reported in $\geq 1\%$ of patients in any treatment regimen) will be provided. PTs will be used for tabulation, sorted by decreasing overall frequency.

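### Read literally, SAP 7.2.2.4 lets an end date after extension entry make an adverse event with an incomplete onset date not treatment-emergent, contrary to SAP 7.1.4.1

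*SAP*

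**What the plan says.** Three parts of the SAP bear on this.

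- **Definition (7.1.4.1).** A treatment-emergent AE (TEAE) "is defined as an AE occurring or worsening on or after the first dose of study medication". For men who enter MBGS206, only AEs "occurring prior to entering the extension study will be considered a TEAE and summarised". The end date plays no part. Protocol 12.1.1 and 13.5.5 also define a TEAE by occurrence or worsening from first dose.
- **Incomplete onset dates (7.2.2.4).** The default is to count the event: "In the event of an incomplete onset date, the event will be considered to be treatment-emergent unless the partial onset date information" shows otherwise. The end date, whole or partial, may also do so. The test is whether either of them "confirms onset or end prior to the first dose of study medication date (or after the date entering the extension study". The bracket is limited to men who continue into the extension.
- **Use in the tables (8.7.1).** "Details for imputing missing or partial start dates of adverse events are described in Section 7.2.2.4".

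Medications and procedures are handled differently at the same boundary. SAP 7.1.4.3 says that "only medications/procedures with a start date prior to entering the extension study will be categorised and summarised". SAP 7.2.2.3 resolves an unclear start around Visit 8 by assuming that it was on or before Visit 8, and calls this a worst-case approach. SAP section 9, on changes from the protocol, lists only the vitamin D cut-off.

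**The concern.** The two time limits in 7.2.2.4 are not mirror images, but one phrase covering onset or end serves both. At the early limit an end date is informative, because an event that is over before first dose must have started before it. At the late limit it is not informative, because an event that ends after extension entry may have started at any time.

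Applied as written, the rule can override a partial onset date that already places the event on treatment. It also reverses the sentence's own default, which is to count an event when its timing is uncertain. The effect would be selective: an event that resolves after entry is dropped, while the same event is kept if it resolves before entry or has no end date recorded.

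At stake are the displays that depend on the TEAE flag in SAP 8.7.1: TEAEs, TEAEs of special interest, related and serious TEAEs, TEAEs by maximum intensity and by causality, and the most common TEAEs.

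**Working it through.** The plan states no figure here, so there is none to reproduce. The check compares two rules on the same events.

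**Illustrative timeline (assumption).** First dose is Day 1. Extension entry is at the end of 24 weeks: 24 × 7 = 168 days, so entry is taken as Day 169.

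**Rule A, 7.2.2.4 as written.** Not a TEAE if onset or end is confirmed before Day 1, or onset or end is confirmed after Day 169.

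**Rule B, onset only at the late limit.** Not a TEAE if onset or end is confirmed before Day 1, or onset is confirmed after Day 169.

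| Partial onset | End date | Rule A | Rule B | What 7.1.4.1 implies |
|---|---|---|---|---|
| Days 57 to 87 | Day 190 | not TEAE | TEAE | TEAE: onset certainly on treatment |
| Days 57 to 87 | Day 150 | TEAE | TEAE | TEAE |
| Days 57 to 87 | none recorded | TEAE | TEAE | TEAE |
| wholly unknown | Day 190 | not TEAE | TEAE | not settled by the dates |
| Days 160 to 189 | Day 195 | not TEAE | TEAE | not settled by the dates |
| Days 175 to 204 | Day 210 | not TEAE | not TEAE | not TEAE: onset after entry |
| Day −40 to Day −10 | Day −5 | not TEAE | not TEAE | not TEAE: over before first dose |

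**Reading the table.**

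1. The rules differ in rows 1, 4 and 5 only. In each, the end date is after entry and onset is not confirmed to be after entry.
2. Row 1 is a direct contradiction. The partial onset date alone puts the event on treatment, so 7.1.4.1 requires it to be counted, and Rule A excludes it.
3. Rows 1 to 3 share the same onset. Only the end date differs, and 7.1.4.1 gives it no role.
4. In rows 4 and 5 the dates do not settle the timing. The default in 7.2.2.4, like the medication rule in 7.2.2.3, would count these events; Rule A does not.
5. Rule B keeps out everything that is properly out (rows 6 and 7).

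**Can such an end date exist?** Extension entrants have their last MBGS205 visit at Visit 8. However, Protocol 12.1.2 says: "All ongoing AEs/SAEs should be followed up until resolution or stabilisation or the last visit", with the last visit as the limit where the investigator thinks resolution unlikely. An end date after entry is therefore possible. The documents do not say whether an AE open at transfer is closed in the MBGS205 or the MBGS206 database.

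**How many men?** SAP 3.1 says: "A minimum of 25 subjects per treatment arm will be invited to participate in a 6 month extension study". That is at least 4 × 25 = 100 men invited. The number who enter is not stated, nor is the number of AEs, of incomplete onset dates or of late end dates. No event count follows.

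**The case against.** The strongest reply is that this is a loosely built sentence whose meaning can be recovered. SAP 7.1.4.1 is the governing definition, and 8.7.1 describes 7.2.2.4 as dealing with start dates. Read with those, the bracket concerns onset after entry, and the word for end serves only the pre-dose limit. The authors may well have meant that. So a reader who infers that the plan will remove these events goes too far: removal happens only if the sentence is programmed literally. What remains is that the literal text gives the wrong class and nothing in the SAP corrects it.

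Four other inferences are tempting and are not supported.

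- **That the lost events are the persistent ones.** An event that starts a few days before Visit 8 and ends a few days after it also qualifies.
- **That they disappear from the report.** SAP 8.7.1 puts all AEs in a comprehensive listing. Its overall summary has rows for any AEs, related AEs, SAEs, severe AEs, and AEs leading to discontinuation or death, none worded as TEAE-only.
- **That they would be counted nowhere because they began too early for MBGS206.** That study has its own analysis plan, which is not available here.
- **That a number of lost events can be given.** Doing so means treating 100 invited men as entrants and guessing the rates of AEs, incomplete onset dates and late end dates.

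It is also fair to say that the AE summaries are descriptive, so no test result depends on this.

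**Conclusion.** The point holds as a defect of wording with a definite wrong result when followed literally. For an extension entrant with an incomplete onset date, an end date after entry is enough to make the event not treatment-emergent, even when the partial onset date places it on treatment. That contradicts 7.1.4.1 and departs from the start-date approach used for medications in 7.1.4.3 and 7.2.2.3.

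The reach is narrow: the TEAE-labelled displays only, and only where an incomplete onset date, entry to MBGS206 and a later end date in the MBGS205 database coincide. The number of events cannot be computed and is probably small. If events open at transfer simply stay ongoing in MBGS205, none is affected. The conclusion rests on the grammar of 7.2.2.4 and on a literal implementation; Day 169 is only illustrative. It is worth correcting because the wrong result is avoidable at almost no cost.

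**What to change.** Reword 7.2.2.4 along these lines: an AE with an incomplete onset date counts as treatment-emergent except where (i) the partial onset date, or the complete or partial end date, shows that it started or ended before first dose; or (ii) for a man who entered MBGS206, the partial onset date shows that it started after entry. The end date then serves the before-first-dose exclusion only.

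It would help to add a line saying in which study's database the end date of an AE open at transfer is recorded.

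The cost is one sentence in the SAP and one line of derivation code, best settled before unblinding. If the code already uses onset alone at the extension limit, the change only brings the text into line with it.

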8 STATISTICAL METHODS

8.1 General statistical conventions

All statistical procedures will be completed using SAS version 9.4 or higher.

8.1.1 Populations for analysis

Demographic and baseline characteristics will be summarised by Safety, ITT and PP populations, unless otherwise stated.

Analyses of the primary efficacy endpoint will be performed on the ITT population, and also on the PP population as a sensitivity analysis.

[figure not shown]
The secondary and exploratory efficacy endpoints will be analysed using the ITT population.

The safety and tolerability variables will be analysed using the Safety population.

PK data will be analysed using the PK population.

8.1.2 Treatment groups

t regimens in the below order:

8.1.3 Descriptive statistics

Continuous variables will be summarised using descriptive statistics including number of non-missing observations (n), arithmetic mean (Mean), median (Median), standard deviation (SD), minimum value (Min), maximum value (Max) and number of missing observations (if any). One additional decimal point for mean and median and 2 additional decimal points for SD will be used.

For categorical variables, summaries will include the number of non-missing observations (n) or the number of patients in the population (N) as applicable, the counts of subjects and percentages. Percentages will be rounded to one decimal place. The number of missing values will be presented as a separate category with no percentage, but only if any missing value is recorded in the data for that summary.

Summary statistics will only be presented at each visit for which the parameter is scheduled to be collected.

8.1.4 Statistical significance

Unless otherwise stated, all statistical testing will be two-sided and conducted at the significance (alpha) level of 0.05. Two-sided 95% confidence intervals (CIs) will be provided when relevant. All four treatment regimens will be assessed by pairwise comparisons, and no adjustment for

multiplicity will be made.

8.1.5 Definition of Baseline

For summary purposes, the baseline value will be defined as the last non-missing value collected prior to the first dose of study medication, unless other specified.

Change from Baseline is defined as (value at assessment date – baseline value).

For Actigraphy Derived Activity and Sleep Parameters, as data is not collected prior to administering the study drug, data collected during the 7 days from Visit 1 will be considered baseline data for all associated analysis.

For Semen quality analysis/parameters, samples at baseline can be taken up to 48 hours after the Baseline Visit. As such baseline will be defined as the last non-missing value collected up to 48 hours post the date of first dose of study medication.

For DXA parameters, assessments at baseline can be taken up to day 8 after the Baseline Visit. As such baseline will be defined as the last non-missing value collected up to 8 days post the date of first dose of study medication.

For selected renal parameters change from Screening will be calculated. Change from Screening will be defined as (value at assessment date – screening value), where the screening value is defined as the last non-missing value collected at a Screening Visit (Day -28 to Day -1).

8.1.6 Data re-allocation

The following general rules to handle repeated assessments will be considered:

- 12-lead ECG:
 - in case of multiple measurements associated to the same timepoint (e.g. triplicate ECGs), the average value will be considered for all post baseline HR, RR interval, PR interval, QRS duration, QT interval, QTcB interval and QTcF interval.
- Semen quality analysis/parameters:
 - in case of multiple measurements associated to the same timepoint as permitted by the protocol the average value will be considered for all post baseline semen parameters.

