To evaluate the effect of BGS649 treatment on semen quality, semen analysis (semen volume, sperm count, concentration, motility and morphology) will be performed. Subjects will be expected to successfully provide semen samples on three occasions during the Randomisation Phase. It is understandable that some subjects will not be able to provide semen samples.

Semen samples will be collected after a minimum of 48 hours of sexual abstinence, therefore no sexual activity should be performed in this time period and no spermicidal cream used to avoid interference with semen evaluation.

Semen PK

Additional semen samples will be required at EOT in order to assess PK in seminal fluid to evaluate the concentration of BGS649 at steady state. Seminal fluid PK will be assessed at Visit 8 (EOT) ([Section 11.3.7](#)). For subjects that are discontinued early from the study drug, an EOT sample will be obtained.

Any subjects who are vasectomised or have vasectomy planned during the study period, will be exempt.

Semen samples at baseline be taken up to 48 hours before or after the Baseline Visit. During Randomisation Phase semen samples may be provided up to 48 hours before or after the Assessment visit.

Testosterone Monitoring:

To ensure adequate safety monitoring, serum total testosterone levels will be evaluated at each visit by an independent unblinded physician (see [Section 9.3.6](#) and [Section 16.3](#)) and if subject meets discontinuation criteria (total testosterone is ≥ 1500 ng/dL (52 nmol/L) at any 2 consecutive time points during the study), the subject will be discontinued from treatment. In addition, if one of the active BGS649 study arms presents with ≥ 2 subjects meeting this discontinuation criterion at any time point within the first 24 randomized subjects to that arm or $> 15\%$ subjects meet this criterion at any time point ≥ 25 randomized subjects, then the arm will be evaluated by the independent DMC for potential dosing discontinuation based on FDA guidance (FDA Advisory Committee Industry Briefing Document Testosterone Replacement Therapy, Sept 2014). Subjects may be discontinued from the study arm and no further randomisation to that arm will be performed.

[figure not shown]

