- Discontinue investigational treatment for a subject if individual serum creatinine increases $\geq 50\%$ compared to Baseline (and is considered clinically significant), or in the event of treatment emergent proteinuria (albumin:creatinine ratio [ACR] >300 mg/g or >30 mg/mmol; protein:creatinine ratio [PCR] ≥ 500 mg/g or >50 mg/mmol). (Creatinine can be repeated once within 7 days of initial alert. Study drug administration should be suspended during this time and resumed only if repeat creatinine is back to pre-alert level)
 - A renal event leading to subject discontinuation should be followed up until event resolution (serum creatinine within 10% of Baseline, protein-creatinine ratio within 50% of Baseline), stabilises or becomes not clinically significant, or is assessed as being chronic.
6. Subject missed 4 or more consecutive study drug dosing.
 7. Development of prostate cancer or PSA increase more than 1.4 ng/ml above Screening level. It is recommended that in these cases subjects undergo urologic consultation.
 8. Haematocrit $>54\%$ (Hematocrit can be repeated once within 7 days of initial alert. Study drug administration should be suspended during this time and resumed only if repeat hematocrit is under 54%)
 9. Development of sleep apnoea.
 10. Development of cardiovascular event (significant arrhythmia acute myocardial infarction, brain stroke, transient ischemic attack, unstable angina, congestive heart failure).
 11. Emergence of the following adverse events:
 - Absolute QTcF >500 msec, or a rise of QTcF of ≥ 60 msec above baseline confirmed by triplicate ECG measurements.
 12. Pregnancy in female sexual partner of the male study subject, occurring after the start of study treatment.
 13. Fragility bone fracture.
 14. Breast cancer.

Procedures for handling patients incorrectly enrolled or randomized

Subjects who fail to meet the inclusion/exclusion criteria must not be enrolled or randomized. If a subject not meeting the study criteria is randomized in error, a discussion must occur between the Medical Monitor and the investigator regarding whether to continue or discontinue the subject from the study. If agreement is reached, the subject should complete the study unless there are safety concerns or if the subject withdraws the consent.

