11.3.7 Semen Analysis

Subjects who are vasectomised or have vasectomy planned during the study period will be exempt from the semen analysis.

Semen Quality

Semen samples will be collected after a minimum of 48 hours of sexual abstinence based on WHO laboratory manual for the examination and processing of human semen. Condoms will not be used for collection as they may contain spermicide affecting quality of the specimen. The analysis will be performed at the study sites for the assessment of semen volume, sperm count, concentration, motility and morphology. Samples may be repeated up to two times at a scheduled time point due to individual variability in semen parameters.

Semen PK

Seminal fluid PK will also be performed at EOT to assess the concentration of BGS649 at steady state (see [Section 11.4](#)).

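### Repeat semen samples are averaged after baseline but not at baseline, which costs some precision and makes the within-arm sperm-category shifts compare a single value with a mean

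*SAP*

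**What the plan says.** - **Repeats are allowed at every scheduled time point.** Protocol 11.3.7: "Samples may be repeated up to two times at a scheduled time point due to individual variability in semen parameters". Nothing limits this to visits after baseline.
- **Baseline is such a time point.** Protocol 9.1.1: "Semen samples at baseline be taken up to 48 hours before or after the Baseline Visit". The schedule of assessments places semen quality analysis at baseline, Week 12 and Week 20.
- **After baseline, repeats are averaged.** SAP 8.1.6: "the average value will be considered for all post baseline semen parameters".
- **At baseline, one value is kept.** SAP 8.1.5, for semen: "baseline will be defined as the last non-missing value collected up to 48 hours post the date of first dose of study medication".
- **Where the baseline is used.** SAP 8.6.4.7 analyses change in each semen parameter to Week 20 by MMRM, with the parameter's own baseline as covariate (SAP 8.6.1). The same section tabulates shifts in sperm-concentration category, counts moves from azoospermia to oligospermia and from oligospermia to normal, and plans a subgroup by whether the baseline sample came before or after first dose.
- **ECG has the same wording.** SAP 8.1.6: "the average value will be considered for all post baseline HR, RR interval, PR interval, QRS duration" and further intervals. The general baseline rule in SAP 8.1.5 applies: "the baseline value will be defined as the last non-missing value collected prior to the first dose of study medication".

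SAP section 9 lists only the vitamin D cut-off as a change from the protocol. No passage averages baseline repeats or explains the difference.

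**The concern.** The protocol allows repeats because one semen sample is a noisy measure of the man. The SAP uses averaging to reduce that noise at every semen time point except the one that anchors every change score. Three things follow for men with repeat baseline samples.

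1. The earlier baseline samples are dropped, so the covariate in the semen MMRMs is noisier than the data allow, and the treatment-difference intervals are somewhat wider.
2. The shift counts compare a single value with a mean. Azoospermia means no sperm at all, so an averaged value is azoospermic only if every sample is zero, whereas the single baseline value needs only one zero. This favours apparent movement out of azoospermia within an arm even when nothing has changed.
3. Because the last value wins and the window runs to 48 hours after first dose, a post-dose sample displaces an available pre-dose one. It also places that man in the post-dose stratum of the timing subgroup.

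**Working it through.** The plan gives no precision, power or variance figure for semen parameters, so there is no figure of its own to reproduce. Its only power calculation concerns the primary endpoint and does not involve this rule.

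**Inputs**
- Up to three samples per time point (one plus two repeats): protocol 11.3.7.
- Baseline samples used under the SAP: m = 1 (SAP 8.1.5). Follow-up samples used: k = all available (SAP 8.1.6).
- Reliability b of one sample (between-man variance as a share of total variance): not given. Assumed range 0.5 to 0.7.
- Share f of men with repeat baseline samples: not given. Shown for 10%, 25% and 50%.

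**Residual variance after baseline adjustment.** Take the single-sample variance as 1 and assume that men within an arm do not differ in true change:

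R(m, k) = [b + (1 − b)/k] − b² / [b + (1 − b)/m]

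| b | k | R(1, k), last value | R(2, k), mean of two | Reduction |
|---|---|---|---|---|
| 0.5 | 1 | 1 − 0.25 = 0.750 | 1 − 0.25/0.75 = 0.667 | 11% |
| 0.6 | 1 | 1 − 0.36 = 0.640 | 1 − 0.36/0.80 = 0.550 | 14% |
| 0.7 | 1 | 1 − 0.49 = 0.510 | 1 − 0.49/0.85 = 0.424 | 17% |
| 0.5 | 2 | 0.75 − 0.25 = 0.500 | 0.75 − 0.333 = 0.417 | 17% |
| 0.6 | 2 | 0.80 − 0.36 = 0.440 | 0.80 − 0.45 = 0.350 | 20% |
| 0.7 | 2 | 0.85 − 0.49 = 0.360 | 0.85 − 0.576 = 0.274 | 24% |

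These reductions apply to men with two baseline samples, not to the trial.

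**Dilution across the trial.** At a given visit the model fits one baseline slope for all men. If a share f has two baseline samples and every man has one follow-up sample, the average baseline variance is V = (1 − f) + f[b + (1 − b)/2], and the residual variance is 1 − b²/V.
- f = 10%: at b = 0.5, V = 0.975 and the residual is 0.7436 against 0.750, a cut of 0.9%. At b = 0.7, V = 0.985 and it is 0.5025 against 0.510, a cut of 1.5%.
- f = 25%: cuts of 2.2% and 3.7%.
- f = 50%: cuts of 4.8% and 7.8%.

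**Shift counts.** For illustration, assume each sample independently has a 50% chance of containing no sperm, and no true change. Take a man with two samples at each time point.
- SAP rule (last baseline value, mean of two later): out of azoospermia 0.5 × (1 − 0.25) = 37.5%; into it 0.5 × 0.25 = 12.5%.
- Mean of two at both: out 0.25 × 0.75 = 18.75%; in 0.75 × 0.25 = 18.75%.

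The SAP rule makes movement lopsided towards improvement; the same rule at both times makes it even. The 50% is chosen only to show the mechanism.

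**How many baseline samples are feasible.** Each sample needs at least 48 hours of abstinence, and the window is 48 hours either side of the visit. Three samples fit only at about −48, 0 and +48 hours, so two is the more realistic case. A rule restricted to pre-dose samples would often leave just one and recover nothing.

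**ECG.** The schedule lists an ECG at baseline without replicates. The protocol's only named triplicate is the on-treatment QTcF check in 9.3.7 ("confirmed by triplicate ECG measurements"), and SAP 8.7.5 summarises ECG change descriptively.

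**The case against.** The strongest reply is that little depends on this. Semen endpoints are exploratory, some men will give no sample, and the loss arises only in men with repeat baseline samples, whose share is unknown. Baseline adjustment also softens the effect of a noisy baseline. All of that stands and limits the size of the point. It does not explain why data collected to reduce noise should be dropped at one time point.

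A reader might also infer more than the documents support:

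- **Bias between arms.** The rule is the same in every arm, and a shift artefact would appear under placebo too. The cost is precision and the reading of within-arm shifts.
- **Gains of 30–40%.** The same formula gives these for three samples at both baseline and follow-up. Three baseline samples fit only at the extremes of the window, so this is not a fair summary.
- **Baseline shifted upward by regression to the mean.** That needs repeats to be prompted by low first results. Protocol 11.3.7 gives variability as the reason and states no such trigger.
- **An unrecognised post-dose baseline.** SAP 8.1.5 states the rule openly, and SAP 8.6.4.7 plans a subgroup by timing. What remains is that a man with both kinds of sample is classed as post-dose.
- **Effects on other models.** Each MMRM uses its own parameter's baseline, so only the semen models are touched.
- **Discarded ECG data.** No baseline replicates are planned, so none is shown to be lost.

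**Conclusion.** The point holds for semen parameters and is minor. The SAP averages repeats after baseline and keeps a single value at baseline, with no stated reason, although the protocol allows repeats at both.

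In men with two baseline samples, averaging would cut residual variance by about 11–17% with one follow-up sample and 17–24% with two. This assumes single-sample reliability of 0.5–0.7 and no variation in true change between men in an arm. Across the trial, with one follow-up sample each, the cut is about 1–8% if 10–50% of men have two baseline samples, and it vanishes if none do. The within-arm sperm-category counts are also tilted towards apparent improvement in men with repeats, by an amount the documents do not allow to be estimated.

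Comparisons between arms are not biased, and the primary endpoint and sample size are unaffected. For ECG there is only a mismatch of wording.

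**What to change.** In SAP 8.1.5 and 8.1.6, before unblinding:

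- Define the semen baseline as the mean of all valid samples within the baseline window the SAP already accepts (up to 48 hours after first dose), under the same averaging rule as at later visits.
- Keep the subgroup by baseline timing. Class a man as pre-dose if he has any pre-dose sample, and use the mean of his pre-dose samples in that subgroup.
- For ECG, reword 8.1.6 so that any baseline replicates that happen to exist are averaged too.

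The cost is one sentence and a derivation change, with no new data. The change does not even out the shift counts for men who gave one baseline sample and several later ones, so the number of samples behind each value should be shown with those tables.
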